9.2.2 Primary Site Procedures and Care

Any procedures on the primary ABSSSI site will be recorded on the eCRF. All ABSSSI site procedures (eg, bedside I&D, operative I&D, aspiration, debridement, re-exam of the lesion in operating room, skin graft, incision without grafting, wound cleaning/lavage, amputation, interventional radiology, other) will be presented on a by subject listing. The percentage of subjects receiving each type of surgical procedure prior to the first dose of test article, from the first dose of test article through to the assessment of Early Clinical Response (Safety and mITT population), from the first dose of test article through to the EOT Visit (Safety, mITT and CE-EOT populations), and through to the PTE Visit (Safety, mITT and CE-PTE populations) will be presented by treatment group. The reasons for the surgical procedures from first dose of test article through the PTE Visit will also be provided for the mITT population.

9.3 Treatment Compliance and Exposure

Exposure summary by treatment group will be presented for the Safety, mITT, and CE-PTE populations. The distribution of subjects by the total number of days on therapy (1 to 3, 4 to 6, 7 to 10, 11 to 12, 13 to 14 and > 14 days) will be presented as will descriptive statistics for the total number of days on therapy.

Treatment compliance is defined as the number of active tablets actually received divided by the number of active tablets expected ($\times 100$) over the time period defined by the first and last dose date. The last dose date is the last day the subject is expected to receive test article based on the length of therapy determined by the Investigator or the actual last date the subject took test article, if s/he prematurely discontinued test article due to treatment failure or an adverse event. Dose 2 can be missed per protocol if it cannot be taken a minimum of 8 hours after Dose 1 and a minimum of 8 hours before the expected time of Dose 3. Descriptive statistics for treatment

compliance and the number and percentage of subjects at least 80% compliant will be presented by treatment group for the mITT and Safety populations.

A summary of compliance with the pre- and post-dose fasting requirements will also be provided. The percent fasting compliance will be determined based on the total doses taken where fasting is required. The percentage of subjects who were < 50%, 50% to < 80%, and 80% to 100% compliance with the pre-dose and post-dose fasting requirements will be summarized for the mITT and Safety populations.

10 EFFICACY PARAMETERS

For all efficacy analyses, subjects will be analyzed in the group to which they were randomized. By definition, subjects who receive the wrong test article are not included in the CE-EOT, CE-PTE, ME-EOT and ME-PTE populations. Subjects who are randomized to the wrong infection type or prior antibiotic stratum will be analyzed in the stratum to which they were randomized, unless otherwise stated. A summary of the efficacy analyses is provided in [Appendix 2](#).

10.1 Primary Analysis

The primary efficacy analyses will be based on the mITT population. The non-inferiority test will be a 1-sided hypothesis test performed at the 2.5% level of significance. This non-inferiority test will be based on the lower limit of the 2-sided 95% confidence interval (CI). The primary efficacy outcome is the percentage of subjects with an Early Clinical Success at 48 to 72 hours after the first dose of test article.

The number and percentage of subjects in each treatment group defined as an Early Clinical Success, Clinical Failure and Indeterminate (subjects with missing data or who are lost to follow-up) will be tabulated, as will the overall category combining Clinical Failure and Indeterminate. The null and alternative hypotheses are as follows:

$$H_0 : p_1 - p_2 \leq -\Delta \text{ and } H_1 : p_1 - p_2 > -\Delta ,$$

where p_1 is the primary efficacy outcome rate in the omadacycline treatment group, p_2 is the primary efficacy outcome rate in the linezolid treatment group, and Δ is the non-inferiority margin of 10%.

To test the null hypothesis, a 2-sided 95% CI for the observed difference in primary outcome rates (omadacycline treatment group minus linezolid treatment group) will be calculated for the mITT population. If the lower limit of the 95% CI for the difference in the mITT population exceeds -10% , then the null hypothesis will be rejected and the non-inferiority of omadacycline to linezolid will be declared.

The 2-sided 95% CI for non-inferiority testing based on the difference of Early Clinical Success rates at 48 to 72 hours after the first dose of test article, will be computed using the method proposed without stratification by Miettinen and Nurminen³. For notation purposes, assume 1 represents the omadacycline group (Group 1) and 2 represents the linezolid group (Group 2).

Based on Miettinen and Nurminen, the 2-sided 95% CI is given by the roots for $RD = p_1 - p_2$ of the following equation:

$$\chi^2_\alpha = \frac{(\hat{p}_1 - \hat{p}_2 - RD)^2}{V}$$

where χ^2_α is the cut point of size α from the chi-square distribution ($\chi^2_\alpha=3.84$ for 2-sided 95% CI); RD is the difference between the 2 true rates ($RD = p_1 - p_2$); \hat{p}_1 = the observed average proportion in Group 1; \hat{p}_2 = the observed average proportion in Group 2; and

$$V = \left[\frac{\tilde{p}_1(1-\tilde{p}_1)}{n_1} + \frac{\tilde{p}_2(1-\tilde{p}_2)}{n_2} \right] \frac{n_1 + n_2}{n_1 + n_2 - 1}$$

where n_1 = number of subjects in Group 1; n_2 = number of subjects in Group 2; $\tilde{p}_1 = \tilde{p}_2 + RD$; and \tilde{p}_2 is the maximum likelihood estimate for p_2 as a function of RD and under the constraint $p_1 = p_2 + RD$.

As stated above, the 2-sided 95% CI for the difference in rates is given by the roots for $RD = p_1 - p_2$ from the equation above, but this equation does not allow for explicit solution for RD . Therefore, a numerical algorithm will be used to obtain the 2 roots (CI) for RD . This CI approach corresponds to the non-inferiority test (a p-value approach) proposed by Farrington and Manning².

The reasons for Clinical Failure and reasons for Indeterminate response will be summarized by treatment group.

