22.4.3 Statistical Model, Hypothesis, and Method of Analysis

To demonstrate the efficacy of omadacycline is non-inferior to linezolid in the treatment of adult subjects with ABSSSI, the following hypothesis will be evaluated by analysis of the Clinical Success rates.

The null hypothesis and alternate hypothesis for the Early Clinical Response endpoint will be assessed in the mITT population as follows:

$$H_0: \theta_T - \theta_C \leq -\Delta$$

$$H_{ai}: \theta_T - \theta_C > -\Delta$$

Where the clinical success rate for the omadacycline regimen is θ_T and for linezolid is θ_C

Δ is the non-inferiority (NI) margin and is 0.10.

Similar null and alternative hypotheses can be set up with Δ of 0.10 for the PTE endpoint. For the Early Clinical Response (FDA) endpoint, a 2-sided 95% confidence interval (CI) approach for the difference of clinical success rates (using the point estimate of the difference: omadacycline response proportion minus linezolid response proportion) will be used to test for the NI of the omadacycline arm compared to the linezolid arm in the mITT population. The 95% CI will be calculated using the unstratified method proposed by Miettinen and Nurminen.⁹ Omadacycline will be considered non-inferior to linezolid if the lower bound of the CI is greater than -0.10.

For Investigator's Assessment of Clinical Response at PTE (EMA) primary efficacy analyses in both the mITT and CE populations, a 2-sided 95% CI approach for the difference of clinical success rates (using the point estimate of the difference: omadacycline response proportion minus linezolid response proportion) will be used to test for the NI of the omadacycline arm compared to the linezolid arm. The 95% CI will be calculated using the stratified (for the randomization stratification factors) method proposed by Miettinen and Nurminen.⁹ Omadacycline will be considered non-inferior to linezolid if the lower bound of the CI is greater than -0.10.

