5.1.2 Randomization and Masking

All eligible subjects will be randomized via an Interactive Response System (IxRS) that assigns them to 1 of the treatment arms (in a 1:1 ratio). The site delegate will contact the IxRS (via phone or web) after confirming that the subject fulfills all the inclusion criteria and none of the exclusion criteria. The IxRS will assign a test article to the subject based on a computer-generated randomization schedule. The randomization will be a blocked randomization sequence stratified by type of infection (wound infection, cellulitis/erysipelas or major abscess) and receipt of an allowed antibacterial therapy in the 72 hours prior to randomization (yes or no). Subjects randomized into the study will be assigned the treatment corresponding to the next available number in the respective stratum of the computer-generated randomization schedule. The subject is considered randomized when the IxRS provides the test article assignment by providing a kit number (ie, completes a randomization transaction), regardless of whether the subject actually receives any medication. Enrollment of subjects with major abscess will be capped at 30% of the subjects randomized. Enrollment of subjects who have received an allowed antibacterial therapy in the 72 hours prior to randomization will be capped at 25% of the subjects randomized.

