10.2 Sensitivity and Additional Analyses of the Primary Efficacy Outcome

Sensitivity analyses of the primary outcome include:

- Determination of the 95% CI adjusted for infection type and receipt of prior antibiotics. If there are < 20 subjects within a stratum and treatment group, or there is a 0 count within a stratum for a treatment group and outcome, wound and abscess will be combined. If the combining of the infection types is not sufficient to complete the adjusted analysis, the prior antibiotic strata will be combined into one group. The 95% CI interval will be computed using the stratified methodology of Miettinen and Nurminen. Cochran-Mantel-Haenszel weights will be used for the stratum weights in the calculation of the CI as follows, where n_{1i} = number of subjects in Group 1 in the i th stratum; n_{2i} = number of subjects in Group 2 in the i th stratum:

$$W_i = \frac{n_{1i}n_{2i}}{n_{1i} + n_{2i}}$$

- The second sensitivity analysis of the primary outcome will consider all subjects who are lost to follow-up prior to a lesion size assessment from 46 to 72 hours or have missing data as an Early Clinical Success (these subjects are considered Indeterminates and analyzed as Clinical Failures in the primary analysis).
- A multiple imputation analysis using a Markov chain Monte Carlo full data imputation will be used to define missing data. Fifty data sets will be created using this technique in which type of infection (cellulitis/erysipelas, major cutaneous abscess and wound infection), prior receipt of antibiotics (yes and no), infection result of IV drug use, (yes and no) and baseline

lesion area ($\leq 300 \text{ cm}^2$, > 300 to 600 cm^2 , > 600 to 1000 cm^2 , and $> 1000 \text{ cm}^2$) are included as predictive variables.

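### The primary Early Clinical Response interval leaves out the randomization strata: valid as planned, slightly wide if the strata predict response; stratifying is an optional improvement

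*SAP*

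**What the plan says.** SAP 5.1.2 describes the allocation: "The randomization will be a blocked randomization sequence stratified by type of infection" (wound infection, cellulitis/erysipelas, major abscess) and by receipt of an allowed antibacterial in the preceding 72 hours, yes or no. That makes six strata. Abscess is capped at 30% of randomized subjects and prior antibacterial use at 25%.

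For the FDA primary endpoint, Protocol 22.4.3 says: "The 95% CI will be calculated using the unstratified method proposed by Miettinen and Nurminen". SAP 10.1 agrees; its interval "will be computed using the method proposed without stratification by Miettinen and Nurminen".

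For the EMA endpoint at PTE, the same protocol section says: "The 95% CI will be calculated using the stratified (for the randomization stratification factors) method proposed by Miettinen and Nurminen".

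For ECR, a stratified interval is already planned as a sensitivity analysis. SAP 10.2 says: "The 95% CI interval will be computed using the stratified methodology of Miettinen and Nurminen", with Cochran-Mantel-Haenszel (CMH) weights. Its collapsing rule acts if a stratum has fewer than 20 subjects in a treatment group, "or there is a 0 count within a stratum for a treatment group and outcome, wound and abscess will be combined". If that is not enough, "the prior antibiotic strata will be combined into one group". Protocol 22.4.4 also lists the adjusted analysis as a sensitivity analysis, and adds a superiority step on the ECR difference.

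**The concern.** Blocking within strata balances the arms on the stratification factors. If those factors predict response, the treatment difference varies less from trial to trial than an unstratified variance assumes. The unstratified interval then includes between-stratum variation that the design has already removed, so its lower bound sits slightly too low. The non-inferiority decision depends on that bound. At stake is a small amount of power that could be had without further patients, using a method the sponsor has already written for this endpoint and uses as primary for the other.

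**Working it through.** **1. The plan's own figure.** Inputs from SAP 5.1.1: 79% success in both arms, margin 10 points, one-sided alpha 0.025, power 90%, Farrington-Manning. The restricted rates at a difference of -0.10 are 0.7316 and 0.8316.

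- s0 = √(0.7316×0.2684 + 0.8316×0.1684) = 0.5800
- s1 = √(2×0.79×0.21) = 0.5760
- n per arm = [(1.960×0.5800 + 1.2816×0.5760)/0.10]² = 351.5, so 352 per arm and **704** in total. This reproduces.
- Power at 352 per arm = Φ[(0.10×√352 − 1.960×0.5800)/0.5760] = 90.04%.

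**2. Assumptions for the strata.** Rates by stratum and the cellulitis/wound split are not in the documents. Assumed: mean rate 79%; abscess 30% and prior antibacterial 25% (both at their caps); wound 20% or 35%; factors independent; infection-type rates equally spaced, in all six orderings. The label 10+5 means 10 points across infection types and 5 points for prior antibacterial.

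**3. Variance removed.** R² is the between-stratum variance divided by 0.79×0.21 = 0.1659, and the standard error shrinks by √(1−R²). Example: 10+5, wound 20% and lowest, cellulitis 50%, abscess 30% and highest.

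- Infection type (points −5, 0, +5; mean 0.5): 0.2×25 + 0.3×25 − 0.5² = 12.25
- Prior antibacterial: 0.25×0.75×5² = 4.69
- R² = 16.94/1659 = 1.02%
- With wound and abscess pooled, the infection-type part falls to 0.25, so R² = 4.94/1659 = 0.30%
- At 20+10 each figure is four times as large: 4.08% and 1.19%

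The approximate unstratified half-width is 1.96×√(2×0.1659/352) = 6.02 points. Over all orderings and both wound shares, six strata narrow it by 0.03 to 0.04 points at 10+5 and by 0.12 to 0.17 at 20+10.

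**4. Simulated power.** True difference 0, 200,000 trials per scenario, score test at −10 points with the restricted estimate and the N/(N−1) factor of SAP 10.1. The Monte Carlo standard error of each power is about 0.07 points; gains are paired within trials.

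| Spread | Gain, six strata (points of power) | Gain, wound and abscess pooled (wound 20%) |
|---|---|---|
| 0+0 | 0 | not shown |
| 10+5 | 0.12 to 0.21 | 0.06 to 0.20 |
| 20+10 | 0.45 to 0.73 | 0.14 to 0.62 |

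Unstratified power is 90.1% to 91.0% throughout. In the example of step 3, power (unstratified / six strata / pooled) is 90.16 / 90.31 / 90.22% at 10+5 and 90.70 / 91.18 / 90.84% at 20+10. A separate run at a more extreme spread (30 points across infection types plus 5; cellulitis 40%, wound 30%, abscess 30%) gained 1.0 point, from 91.1% to 92.1%.

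**5. Simulated one-sided error.** True difference −10 points in every stratum, 400,000 trials, standard error 0.025 points. At the non-zero spreads it is 2.23% to 2.50% unstratified. It is 2.44% to 2.56% when stratified with pooling of any stratum below 40 subjects in total. The unstratified test is at or below its nominal 2.5%.

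**6. Small strata.** Wound with prior antibacterial: 704×0.20×0.25 = 35 subjects, about 18 per arm, even with prior use at its cap. This is below the SAP's 20 per arm and also below 40 in total. It falls under 40 whenever the wound share is below 40/(704×0.25) = 23%. With shares below the caps (wound 20%, abscess 20%, prior antibacterial 15%) and wound and abscess the two extremes, pooling is certain and the gain is only 0.03 to 0.07 points.

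**The case against.** The strongest case against is that nothing is broken. Protocol and SAP agree, and the interval corresponds to the Farrington-Manning test behind the sample size. The stratified ECR interval will be reported in any event, so the only question is which of two planned analyses is primary. The gain is a few hundredths to under two tenths of a point of half-width against a 10-point margin, on assumed stratum rates. An unstratified interval needs no pooling rule and is unaffected by subjects randomized to the wrong stratum, which SAP 9.2 and 10 anticipate. All of this stands, and it is why the point is optional.

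Three stronger readings are tempting but not supported.

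- **That the plan is in error, or that stratified randomization obliges a stratified primary interval.** The error rate is not inflated and the stated power reproduces.
- **That the SAP 10.2 collapsing rule must change if its interval becomes primary.** Its triggers use per-arm and outcome counts, which cannot be read while blinded. But a fixed algorithm run by program after unblinding is still prespecified, and SAP 6.2.2 already completes treatment-dependent determinations that way. A blinded trigger is cleaner, not necessary.
- **That the zero-count trigger will usually fire.** Its frequency depends on the assumed direction of the prior-antibacterial effect. It also depends on whether outcome means success versus non-success or the three categories of SAP 10.1 ("defined as an Early Clinical Success, Clinical Failure and Indeterminate"). The documents settle neither.

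Dropping the zero-count trigger could be feared to leave a stratum with no variance. With 26/26 successes in both arms, the variance at a difference of −10 points is (0.9×0.1/26)×(52/51) = 0.0035. At a difference of 0, relevant to superiority, it is zero, but only for that stratum's term; the overall stratified interval can still be computed.

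**Conclusion.** The point holds as an optional improvement. The primary ECR analysis is valid and adequately powered as written. If the strata predict response, its interval is slightly wide and its test slightly conservative. Stratifying would gain 0 to about 0.7 points of power for assumed spreads up to 20 points across infection types plus 10 for prior antibacterial use. The gain is nothing if the strata do not predict response, and it is smaller if wound and abscess are pooled. The direction is a general statistical result; the size rests on assumed rates and shares. Keeping the current plan is defensible.

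**What to change.** If the sponsor wishes to make the change, do it before unblinding:

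1. In SAP 10.1 and Protocol 22.4.3, make the stratified Miettinen-Nurminen interval of SAP 10.2 (as-randomized strata, CMH weights) the primary ECR analysis. Keep the unstratified interval as the sensitivity analysis.
2. Amend Protocol 22.4.4 to match, and state that the same stratified interval governs the superiority step. Say also which method the supportive ECR analyses in SAP 10.2 and 10.4 use.
3. Preferably, replace the collapsing trigger with one on total mITT stratum size. For example, if any stratum has fewer than 40 subjects in both arms together, combine wound and abscess; if any is still below 40, combine the prior-antibacterial strata. The threshold is a choice. Such a rule can be read blinded and does not depend on outcome counts.

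**Cost.** No added patients. The protocol change needs an amendment under Protocol 29.1, with sponsor, ethics-board and, where required, health-authority approval, at about 50 sites. An entry in SAP section 7 instead would make the SAP depart from a protocol it now matches. Pooling may remove part or most of the gain. If prior antibacterial use is only 10% (wound and abscess 30% each), the second collapsing step fires in 99% of simulated trials. The change is therefore best made alongside another amendment, not as the reason for one.

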10.2 Sensitivity and Additional Analyses of the Primary Efficacy Outcome

Sensitivity analyses of the primary outcome include:

- Determination of the 95% CI adjusted for infection type and receipt of prior antibiotics. If there are < 20 subjects within a stratum and treatment group, or there is a 0 count within a stratum for a treatment group and outcome, wound and abscess will be combined. If the combining of the infection types is not sufficient to complete the adjusted analysis, the prior antibiotic strata will be combined into one group. The 95% CI interval will be computed using the stratified methodology of Miettinen and Nurminen. Cochran-Mantel-Haenszel weights will be used for the stratum weights in the calculation of the CI as follows, where n_{1i} = number of subjects in Group 1 in the i th stratum; n_{2i} = number of subjects in Group 2 in the i th stratum:

$$W_i = \frac{n_{1i}n_{2i}}{n_{1i} + n_{2i}}$$

- The second sensitivity analysis of the primary outcome will consider all subjects who are lost to follow-up prior to a lesion size assessment from 46 to 72 hours or have missing data as an Early Clinical Success (these subjects are considered Indeterminates and analyzed as Clinical Failures in the primary analysis).
- A multiple imputation analysis using a Markov chain Monte Carlo full data imputation will be used to define missing data. Fifty data sets will be created using this technique in which type of infection (cellulitis/erysipelas, major cutaneous abscess and wound infection), prior receipt of antibiotics (yes and no), infection result of IV drug use, (yes and no) and baseline

lesion area ($\leq 300 \text{ cm}^2$, > 300 to 600 cm^2 , > 600 to 1000 cm^2 , and $> 1000 \text{ cm}^2$) are included as predictive variables.

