17.2 Assessment of Lesion Size

Lesion measurements by ruler should be performed by the Investigator at Screening, and every scheduled evaluation with the exception of the Final Follow-up assessment (see [Section 8](#)).

Surface area of lesions will be calculated by multiplying the head-to-toe maximum length of total lesion and maximum width (perpendicular to maximum length) inclusive of contiguous involvement (erythema, edema and/or induration). Investigator ruler measurements will be used to document lesion size. Instructions for ruler measurements will be provided to the investigator.

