5.1.1 Sample Size

The study is designed to show NI in the primary efficacy outcome of Early Clinical Response at 48 to 72 hours following the first dose of test article in the modified Intent to Treat (mITT) population. An NI margin of 10% will be used for the analysis in the mITT population. The NI margin was based on an analysis of the historical data regarding the treatment effect of antibiotics in ABSSSI.

In the po study of tedizolid versus linezolid, the rates of Early Clinical Response (ECR) were 79% in both treatment arms in the ITT population¹. Thus, an outcome rate of 79% in the mITT population was used for determination of the sample size. For the ECR primary efficacy endpoint, assuming an outcome rate of 79% for both treatment groups, NI margin of 10%, 90% power and a 1-sided alpha of 0.025, using the sample size determination method of Farrington and Manning², a total of 704 subjects are required.

The rates of clinical success based on the Investigator’s Assessment at PTE were 86% in the ITT population and 95% in the CE population for linezolid, in the recent po clinical study in ABSSEI subjects¹. To be conservative, outcome rates of 85% in the mITT and 90% in the CE population are used for the sample size determination. Assuming an 85% outcome rate in both treatment groups, NI margin of 10%, and a 1-sided alpha of 0.025, with a total of 704 subjects, there is more than 90% power to show NI for Investigator’s Assessment of Clinical Response at PTE in the mITT population. With an evaluability rate of 80%, there will be 564 subjects in the CE population. Assuming a 90% outcome rate in both treatment groups, NI margin of 10% and a 1-sided alpha of 0.025, 564 subjects provides more than 90% power to show NI in the CE population.

Thus, a total of 704 subjects provide sufficient power for the primary efficacy analyses for both the FDA and EMA regulatory authorities. A summary of the sample size calculations and assumptions is provided in Table 1.

Table 1. Sample Size and Power Calculations

	Primary Efficacy Outcome FDA (Early Clinical Response)	Primary Efficacy Outcome EMA (Investigator’s Assessment of Clinical Response at PTE)	
Population	mITT	mITT	CE
N	704	704	564
Outcome Rate	79%	85%	90%
Evaluability Rate	N/A	N/A	80%
Power	90%	96%	97%

CE = clinically evaluable; EMA = European Medicines Agency; FDA = United States Food and Drug Administration; mITT = modified intent-to-treat; N = number; N/A = not applicable; PTE = post therapy evaluation.

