Subjects with missing data such that a response cannot be determined will be considered an indeterminate response. Since indeterminates are included in the denominator of the calculation of Early Clinical Success, these subjects are essentially Early Clinical Failures. For the mITT population, the proportion of mITT subjects with an Early Clinical Success is defined using the following formula:

$$\frac{\text{Number of subjects with an Early Clinical Success}}{\text{Number of subjects with an Early Clinical Failure} + \text{Number of subjects with a response of Indeterminate} + \text{Number of subjects with an Early Clinical Success}}$$

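### The multiple-imputation sensitivity analysis of Early Clinical Response uses only baseline predictors and leaves out the Day 2 lesion area that the trial already collects

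*SAP*

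**What the plan says.** SAP 5.2.1 derives Early Clinical Response by program from the change in lesion area since Screening. On missing data it states: "Subjects with missing data such that a response cannot be determined will be considered an indeterminate response". SAP 8.3 makes this concrete: a length or width absent at baseline, or absent in the 46 to 72 hour window, makes the subject Indeterminate.

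Three treatments of these subjects are planned:

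- The primary analysis (SAP 5.2.1 and 10.1) keeps them in the denominator, so they count as failures.
- One sensitivity analysis in SAP 10.2 counts them all as successes.
- Another reads "A multiple imputation analysis using a Markov chain Monte Carlo full data imputation will be used to define missing data". The predictors follow: "Fifty data sets will be created using this technique in which type of infection", then "prior receipt of antibiotics (yes and no), infection result of IV drug use, (yes and no) and baseline" lesion area, cut at 300, 600 and 1000 cm².

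No post-baseline variable is listed. Treatment arm is not listed either, and imputation by arm is not mentioned. The SAP does not name the variable to be imputed, its distribution, or how the 50 results become one interval.

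Protocol 17.2 says: "Lesion measurements by ruler should be performed by the Investigator at Screening, and every scheduled evaluation with the exception of the Final Follow-up assessment". The schedules in Protocol Section 8 and SAP Appendix 1 both show a lesion measurement on Day 2.

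**The concern.** The endpoint is a change in lesion area, and the area on Day 2 is measured roughly a day before the missing value. It is the most direct information on what the missing value would have been. A model restricted to baseline items assumes that, given the baseline profile, missing the visit has nothing to do with how the lesion behaved after dosing. That is a strong assumption. Two subjects with the same baseline profile, one with a lesion that grew by Day 2 and one with a lesion that halved, receive the same imputed success probability.

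The other two treatments of missing data are the extremes: all failures and all successes. Imputation is the only planned analysis between them, so it is the one a reader would take as the plausible case. If it mainly restores the average rate, it tests little.

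The absence of treatment arm matters for a separate reason. If both arms are imputed from one pooled model, imputed outcomes pull the estimated difference towards zero. That helps a non-inferiority claim whenever the observed difference is against omadacycline.

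**Working it through.** **1. The plan's own figure.** SAP 5.1.1 gives "assuming an outcome rate of 79% for both treatment groups, NI margin of 10%, 90% power and a 1-sided alpha of 0.025" and concludes that "a total of 704 subjects are required". With Farrington-Manning, the restricted estimates under the null are 0.7316 and 0.8316, so

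n per arm = [1.96 × √(0.7316 × 0.2684 + 0.8316 × 0.1684) + 1.2816 × √(2 × 0.79 × 0.21)]² / 0.10² = 351.5, rounded up to 352, total 704.

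This matches. The 79% rate and 352 per arm are used below.

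**2. What Day 2 area could add (closed form).** Assume that log area ratios at Day 2 and at 48 to 72 hours are bivariate normal with correlation r, and that 79% meet the 20% rule. For a subject exactly at the 90th percentile of the Day 2 ratio (the boundary of the slowest tenth, not the average within it):

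P(success) = Φ[(0.806 − 1.282 r) / √(1 − r²)]

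This gives 0.576, 0.519, 0.449 and 0.358 for r = 0.5, 0.6, 0.7 and 0.8. A baseline-only model gives about 0.79 whatever r is.

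**3. Simulation of the listed model.** The setting was 704 subjects, 50 imputations and 200 repeats, with a Bayesian linear imputation of the response. Assumed, because the documents give no figures: the slowest 20% on Day 2 count as growing; 12% of them and 4% of the others miss the 48 to 72 hour measurement. That is about 5.6% missing overall, with about 17 growing dropouts.

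| r | True success rate, growing dropouts | Imputed, four listed predictors | Imputed, Day 2 added |
|---|---|---|---|
| 0.3 | 65% | 79% | 67% |
| 0.5 | 56% | 79% | 58% |
| 0.7 | 41% | 79% | 51% |

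Adding Day 2 closes most of the gap. The part left at r = 0.7 comes from fitting a straight line to a yes/no response, which is a reason to impute the area itself.

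**4. Effect on the lower 95% limit.** These are Miettinen-Nurminen limits with 352 per arm and 79% success among everyone else. Expected counts are plugged in, without between-imputation variance. The dropout numbers are assumed.

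| Growing dropouts, omadacycline vs linezolid | Imputed at 79% | At 50% to 35% | All failures (primary rule) |
|---|---|---|---|
| 10 vs 10 | −6.04% | −6.12% to −6.16% | −6.25% |
| 15 vs 5 | −6.04% | −6.94% to −7.41% | −8.49% |
| 25 vs 5 | −6.04% | −7.81% to −8.72% | −10.83% |

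The shift is about 0.1 points when balanced (0.08 to 0.12), 0.9 to 1.4 points at 15 vs 5, and 1.8 to 2.7 points at 25 vs 5. The 35% end is below the 41% to 65% of step 3. At 65%, the point difference moves by (15 − 5) × 0.14 / 352 = 0.4 points, or (25 − 5) × 0.14 / 352 = 0.8 points. If the excess were in the linezolid arm, the limit would move the other way.

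**5. If the yes/no response were imputed by a normal model.** Unrounded draws keep the mean at 0.79. Rounding at 0.5 gives Φ(0.29 / √(0.79 × 0.21)) = 0.762, which is 2.8 points lower among imputed subjects. At an assumed 5% missing this is 0.05 × 2.8 = 0.14 points per arm, and it largely cancels in the difference when missingness is similar in both arms.

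**The case against.** The best defence is scope. This is one supportive analysis, and Protocol 22.4.4 does not list it among its sensitivity analyses. The primary test counts every Indeterminate as a failure. In the unbalanced cases above that rule is already harsher (−8.5% and −10.8%) than the better imputation would be (−6.9% to −8.7%). SAP 5.2.1 also classifies as failures, before any imputation, those stopped for inadequate response with rescue needed, those stopped for an adverse event with rescue needed, and deaths. That removes many subjects with growing lesions from the imputed group. Subjects never dosed, or with no post-baseline measurement, gain nothing from a Day 2 predictor. All of this stands, and it limits the size of the point.

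A reader might go further and infer that the plan fits a multivariate-normal model to a yes/no outcome and must round the draws. The documents do not say so. SAP 10.2 names only Markov chain Monte Carlo, and SAP 8.1 names only SAS. Because SAP 8.3 defines missing data through absent lesion measurements, imputing the area and then applying the 20% rule is an equally open reading. Nor does the SAP say that the Miettinen-Nurminen interval is applied to the imputed data sets. What can be said is that the model is under-specified. Step 5 shows that the normal-model reading, even if right, does little harm.

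The defence does not answer the main point. On either reading the listed predictors are all baseline items, and a better predictor is already in the database.

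**Conclusion.** The point holds as a modest improvement to one sensitivity analysis. As written, a subject with a missing 46 to 72 hour measurement and a lesion growing on Day 2 is imputed at about the average rate for the same baseline profile (about 79%). Under assumed correlations of 0.3 to 0.7 the rate would be 65% to 41%. The effect on that analysis's lower limit is about 0.1 points with balanced dropouts and about 1 to 2.7 points under the assumed imbalances with success rates of 50% to 35%.

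The missing rate, the share of growing lesions, the correlation and the imbalance are all assumptions. A reader might infer that the non-inferiority conclusion is at risk. The documents do not support that, because the primary rule does not depend on the imputation.

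**What to change.** Rewrite the imputation item in SAP 10.2 to state:

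- **Imputed variable:** log lesion area at 46 to 72 hours, by a regression or fully conditional model, only for subjects not already classed as failures under SAP 5.2.1. State how an area of zero is handled on the log scale.
- **Predictors:** continuous log Screening area, log Day 2 area, log Day 7 area where present, infection type as a class variable, prior antibiotic and IV drug use.
- **Arm:** impute separately by treatment arm, or include arm in the model.
- **Derivation and pooling:** apply the 20% rule in each of the 50 data sets, then combine the differences in success rates and their variances by Rubin's rules.

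The cost is SAP wording and a different procedure statement, settled before unblinding. All the variables are already collected.
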